4.4.1.1. Ocular Surface Complications

Under the Protocol NVG14L127, *ocular surface complication* is defined as the occurrence of any AE defined as corneal ulceration, corneal perforation, loss of visual acuity, or ocular infection.

4.4.1.1.1. Ocular Infection

Ocular infection is defined as any ocular events (location reported as "ocular") under SOC "Infections and infestations."

4.4.1.1.2. Corneal Perforation

Corneal perforation is defined as PT of "Corneal perforation."

4.4.1.1.3. Corneal Ulceration

Corneal ulceration is defined as PT of "Ulcerative keratitis."

4.4.1.1.4. Loss of Visual Acuity

Loss of visual acuity is defined as all PTs under HLT "Visual impairment and blindness" except for PT of "colour blindness".

The list of AEs will be reviewed based on the above four definitions via a data review meeting.

4.4.1.2. Serious Adverse Event

An AE will be counted as a *serious adverse event* (SAE) if the Clinical Investigator selected "Yes" to the question 'Is the adverse event serious?' on the AE eCRF. A serious AE may occur during any study phase (ie, baseline, treatment, or follow-up). SAE must fulfil one or more of the following criteria:

- Results in death
- It is immediately life-threatening*
- It requires in-subject hospitalization or prolongation of existing hospitalization
- It results in persistent or significant disability or incapacity
- Results in a congenital abnormality or birth defect
- It is an important medical event that may jeopardize the subject or may require medical intervention to prevent one of the outcomes listed above (including sight-threatening** events and cancer or neoplasm of any type).
- * Herein 'Life-threatening' refers to an event in which the subject was at immediate risk of death at the time of event; it does not refer to an event which hypothetically might have caused death.
- ** Similarly 'Sight-threatening' refers to an event in which the subject was at immediate risk of losing sight; it does not refer to an event which hypothetically might have caused losing of sight.

Serious ocular adverse events include, but are not limited to the following adverse events which are considered to be sight-threatening and are to be reported as SAEs (medically important criteria):

- Adverse Events that caused a decrease in visual acuity > 6 lines (compared with the last assessment of visual acuity at the last visit)
- Adverse Events that caused a decrease in visual acuity to the level of Light Perception or worse
- Adverse Events that required surgical intervention or laser to prevent permanent loss of sight
- Adverse Events associated with severe intraocular inflammation (i.e., 3+ anterior chamber cell/flare or 3+ vitritis)
- Corneal perforation
- Adverse Events that, in the opinion of the investigator, may require medical intervention to prevent permanent loss of sight

4.4.1.3. Case of Special Interest (CSI)

The following cases are the AEs considered to be of special interest by the sponsor:

- > CSI related to AEs requiring (24 h) reporting to the sponsor:
 - Corneal ulceration
 - Decrease in visual acuity of 3 to 6 lines (compared with the last assessment of visual acuity at the last visit)
- ➤ CSI related to medication error: Any unintentional error in the prescribing, dispensing, or administration of a medicinal product while in the control of the healthcare professional or subject
 - Overdose of study drug: Administration of a quantity of a medicinal product exceeding the dose defined in the study protocol.
 - Misuse of study drug: Situations where the medicinal product is intentionally and inappropriately used not in accordance with the study protocol.
 - Abuse of study drug: Persistent or sporadic, intentional excessive use of medicinal product which is accompanied by harmful physical or psychological effects.
 - Other

4.4.1.4. Ocular Adverse Event

An AE will be counted as an *ocular AE* if the Clinical Investigator selected "OD", "OS", or "OU" under 'Eye(s) affected' on the AE eCRF.

4.4.1.5. Adverse Drug Reactions (ADR)

An AE will be counted as an *adverse drug reaction* (ADR) if the Clinical Investigator answered 'Related' to the AE eCRF question "Relationship to Study Drug".

4.4.2. Other Safety Measures

Table 2 lists the safety measures to be evaluated for this study.

Table 2. Safety Assessments

Safety Measures	Note
Intraocular pressure (IOP)	IOP will be measured on both eyes at Baseline, Month 12, Month 24, and Month 36.
Best-corrected distance visual acuity (BCDVA)	BCDVA will be measured for each eye at Baseline, Month 6 and Month 12 in Period 1 and at Month 18, Month 24, Month 30, and Month 36 in Period 2 using a Snellen chart.
	BCDVA in Snellen scale will be converted to logMAR scale using the following equation and be used in all the BCDVA analyses:
	$LogMAR VA = -log_{10} \left(\frac{Snellen numerator}{Snellen denominator} \right)$
Slit-lamp Biomicroscopy	Slit-lamp biomicroscopy examinations will be performed at Baseline, Month 6 and Month 12 in Period 1 and at Month 18, Month 24, Month 30, and Month 36 in Period 2. Grading of the Meibomian glands, lids, lashes, conjunctiva, tear film debris, anterior chamber and lens will be done on an ordinal scale. Cataract severity will be assessed for phakic eyes only.

4.5. Other Definitions

4.5.1. Prior and Concomitant Medications

Non-study medications will be categorized into prior medications and concomitant medications. Specifically, *prior medication* is defined as any non-study medication taken and ended prior to the study medication start date. *Concomitant medication* is defined as any non-study medication taken concurrently while receiving study medication, i.e., the treatment period (period of time from first dose to last dose) of a concomitant medication taken by a subject must overlap with the treatment period (period of time from first dose to last dose) of the study medication.

All prior and concomitant medications will be coded using the World Health Organization (WHO) Drug Global, Version September 2019, format B3. Each prior or concomitant medication will be classified using the Anatomical-Therapeutic-Chemical (ATC) classification system and mapped to a WHO Drug preferred drug name.

4.5.2. Concurrent Medical Conditions

Concurrent medical conditions are those ongoing conditions or diseases that are present at the signing of informed consent.

5. GENERAL CONSIDERATIONS

All measures will be summarized for Overall subjects in Period 1 and by treatment group in Period 2 as well as for the entire study descriptively. Continuous variables will be summarized using descriptive statistics such as number of observations (n), mean, standard deviation, median, minimum, and maximum. Categorical variables will be tabulated using frequency (n) and percent (%).

Unless otherwise specified, the following conventions on decimal places will be followed in reporting numerical results.

Statistic	Reporting Decimal Places
Range (Low Value, High Value)	Recorded decimal places
Mean, Median	Recorded value + 1 decimal places
Confidence interval, standard deviation, standard error	Recorded value + 2 decimal places
P-value	4 Decimal places (ex. 0.0021)

No statistical testing will be conducted for both the efficacy and safety measures for Period 1 in this study.

All data summary/analysis will be performed using SAS Version 9.4 or later. Individual data, including relevant derived variables, will be listed. Additional analyses not specified in this SAP may be conducted if deemed necessary and will be documented in the CSR.

5.1. Adjustments for Covariates

For better understanding the long-term efficacy of IKERVIS, model based analysis (MMRM) will be conducted with corresponding baseline of each endpoint and geographic region (Europe vs. non-Europe) as covariates. The detail of each model will be described in Section 8.

5.2. Handling of Missing Data

No imputation for missing data will be performed on any efficacy and safety endpoints. Unless specified otherwise, descriptive summaries will be based on observed cases.

Completely or partially missing onset and resolution dates for AEs, Concomitant Medications (CM), and Medical History (MH) will be imputed in a conservative fashion as follows:

Incomplete Adverse Event Onset Date

- 1. Year imputation
 - o If *year* is missing (or AE onset date is completely missing), then the onset date will not be imputed.
- 2. Month imputation
 - o If *year* is not missing but *month* is missing, then:

- If *year* = year of first study dose date, then set the *month* and *day* to the day and month of first study dose
- Else if $year \neq year$ of first study dose: set *month* to January

3. Day imputation

- o If day is missing (month and year not missing), then:
 - If year = year and month = month of first study dose, then set day to day of first study dose
 - Else if $year \neq year$ and $month \neq month$ of first study dose, then set day to first day of the month in the year

Incomplete Adverse Event Resolution Date

Do not impute if any resolution date is missing.

If the duration of AE is needed, the following approach may be considered:

- o If year is missing (or AE resolution date is completely missing): do not impute
- o If *year* is not missing but *month* and *day* are missing: impute December 31st for missing *month* and *day*
- o If *year* and *day* are not missing but *month* is missing: impute December for missing *month*
- o If *year* and *month* are not missing but *day* is missing: impute last day of the *month* for missing *day*.

Incomplete CM or MH Onset Date

- 1. If year is missing (or CM/MH onset date is completely missing), do not impute
- 2. If *year* is not missing but *month* and *day* are missing, impute January 1st for missing *month* and *day*
- 3. If year and day are not missing but month is missing, impute January for missing month
- 4. If year and month are not missing but day is missing, impute 01 for missing day

Incomplete CM or MH Resolution Date

- 1. If a resolution date is completely missing, do not impute.
- 2. If year is not missing but month and day are missing, use the last day of the year to impute the missing month and date parts of the resolution date.
- 3. If year and month are not missing but day is missing, use the last day of the month to impute the missing date part of the resolution date

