4.4. Safety-Related Definitions

4.4.1. Adverse Event

Under the Protocol NVG14L127, an adverse event is any untoward medical occurrence in a clinical investigation subject administered a study drug. An AE does not necessarily have a causal relationship with the study drug. For this study, the study drugs are IKERVIS® and Vehicle. Regardless of causality to the study treatment, an AE can be an unintended sign (including an abnormal laboratory finding), symptom, or disease temporally associated with the use of study treatment.

An *on-study* AE can occur any time after the date of informed consent through the last study visit. An AE will be considered as *treatment-emergent* if the onset date of the AE occurred on or after the treatment start date of the analysis period. Treatment-emergent AEs (TEAEs) are a subset of on-study AEs. Both on-study and TEAEs will be collected, but only TEAEs will be tabulated.

The severity of each AE will be graded by the Clinical Investigator as Mild, Moderate, or Severe. AEs will be rated by the Investigator as to their causality/relationship to the study drug.

Each AE will be classified into a system organ class (SOC) and coded to a preferred term (PT) using Medical Dictionary for Regulatory Activities (MedDRA), version 23.1 published in 2020.

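### SAP 5.2's rules for partial AE onset dates are not conservative for Period 2 or for undated events: no Period 2 anchor, a gap in the missing-day branch, and no fallback for a blank onset

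*SAP*

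**What the plan says.** SAP 5.2 says that incomplete dates "will be imputed in a conservative fashion as follows"; Protocol 13.8 had left the detail to the SAP. For AE onset the rules are:

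- **Year missing, or no date at all:** "then the onset date will not be imputed".
- **Month missing:** in the first-dose year, use the first-dose day and month. In any year other than that "of first study dose: set *month* to January".
- **Day missing:** "If year = year and month = month of first study dose, then set day to day of first study dose". The only other branch requires both the year and the month to differ from those "of first study dose, then set day to first day of the month in the year".

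SAP 4.4.1 calls an AE treatment-emergent "if the onset date of the AE occurred on or after the treatment start date of the analysis period", and "only TEAEs will be tabulated". SAP 4.1.2 gives Period 2 its own treatment start, the first double-masked dose or the Month 12 visit. SAP 9.1 analyses ocular surface complications, a primary safety endpoint, by arm within Month 13-24, 25-36 and 13-36 and by time to first onset. It also says that missing data will not be imputed.

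**The concern.** TEAE status is defined period by period, but the date rules know only one dose. A partial date that could lie on either side of the Period 2 start is pushed to its earliest value. That is conservative for Period 1 and for the entire study, because the event stays on treatment. For Period 2 it takes the event out of the randomised, masked comparison.

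The missing-day rule also fails to cover all cases, and a blank onset has nothing to be compared with the treatment start. At stake are the Period 2 TEAE tables by arm and, if the date rules apply to them, the period, arm and onset time of ocular surface complications. SAP 9.1 itself makes the Cox analysis of complications conditional on enough events, so one or two misplaced events could show.

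**Working it through.** The plan gives no number or share of partial AE dates, so there is no figure to reproduce. The check applies the written rules to every possible date.

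**Inputs.** Onset rules from SAP 5.2; TEAE rule from SAP 4.4.1; Period 2 start set at Day 360 and follow-up to Day 1080 (schedule of assessments). First doses run from 1 February 2019 to 31 January 2020, inferred from the Protocol synopsis (first patient February 2019, last completion February 2023). First-dose dates and event times are assumed uniform. Every percentage applies only to events with the stated date part missing.

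**(a) Month missing.** Period 2 covers Days 360 to 1080, which is 1080 − 359 = 721 days. Where the rule names January without a day, 1 January is taken. An event is then dated before Period 2 if it falls in the calendar year in which Period 2 starts, so

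share = (days from Period 2 start to 31 December) / 721.

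- Example: first dose 15 March 2019, Period 2 start 8 March 2020. From 8 March to 31 December is 299 days; 299/721 = 41%.
- Average over all first-dose dates: 182/721 = 25%.
- Range: 0% (Period 2 starts on 1 January) to 364/721 = 50%.

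If the literal missing-day rule is applied after January has been set, 22.2% are dated in Period 1 and a further 8.5% have no rule for the day.

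**(b) Day missing, literal wording.** Neither branch covers another month of the first-dose year, or the first-dose month of a later year.

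- Example, same subject: April to December 2019, March 2020 and March 2021 have no rule, which is 9 + 1 + 1 = 11 of 36 calendar months.
- Range over first-dose dates: 2 to 14 months, out of 36 or 37 in the study.
- Share of events without a rule: 49% of true Period 1 events and 7.7% of true Period 2 events, or 21% overall.

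Most of these months still fix the period. In the example, April to December 2019 is Period 1 and March 2021 is Period 2 whatever the day; only March 2020 straddles the boundary. On average there are 7.9 uncovered months per subject, of which 0.8 is the Period 2 start month (0.8/7.9, about 10%). Day 360 falls in the first-dose month one year later for 77% of first-dose dates. Over the ±7-day visit window this runs from 54% (Day 353) to 100% (Day 367).

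**(b) Day missing, read as a plain else.** The gap closes, but 2.0% of true Period 2 events (0% to 4.2%) are set to the first of the month, before Period 2 starts. In the example, onsets on 8 to 31 March 2020 become 1 March: 24/721 = 3.3%. A plain else therefore does not replace a Period 2 anchor.

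**(c) Year missing.** SAP 5.2 leaves the onset blank; SAP 4.4.1 requires an onset on or after a start date; only events that qualify are tabulated; SAP 9.2 lists non-TEAEs. No section says that an undated AE counts as treatment-emergent.

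**Effect of a Period 2 anchor.** With dates compatible with the Period 2 start set to that start, 0% of true Period 2 events leave Period 2. Before any limit from other dates, 4.1% of day-missing and 50.9% of month-missing true Period 1 events move into it.

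**The case against.** **The anchor is ambiguous.** SAP 5.2 does not define the first study dose, and SAP 4.1.3 and 4.4.1 use period-specific starts. If it was meant per period, (a) falls. The open-label reading is still the natural one, because SAP 4.1.2 and 5.5 name Period 2 when they mean its first dose. Points (b) and (c) do not depend on it.

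**The second branch is a drafting slip.** Very likely: it follows an else-if, and the rule for medications and medical history simply imputes day 01. A reader might infer that the gap removes many events from Period 2. It does not: it falls mainly on Period 1, and a recorded month and year usually settle the period. A day is still needed for time to onset.

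**Undated AEs are not deleted.** A reader might infer that they vanish from the report. The documents do not support that: non-TEAEs are listed, and the SAP never states how a blank onset is classified. Exclusion from the tables is an inference from SAP 4.4.1.

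**The complications may be untouched.** SAP 9.1 rules out imputation for them, and SAP 5.2 opens by ruling it out for all safety endpoints before giving the date rules. Onset date is a reported item for every AE (Protocol 12.2.4.1), corneal ulceration, perforation and marked acuity loss need reporting within 24 hours, and the complication list goes to a data review meeting. Badly incomplete dates should be rare there. This lowers the likely impact, but leaves open which rule governs.

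**Bias towards one arm** might also be inferred. The rules do not use the arm, so none is shown.

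**Conclusion.** The point holds as a defect of the written rules: followed as they stand, they are not conservative for Period 2 or for undated events, and no other section repairs them. About 25% of month-missing Period 2 events (0% to 50% by first-dose date) are dated before Period 2. Between 2 and 14 of 36-37 calendar months have no missing-day rule, mostly in Period 1, with the period truly in doubt only in the Period 2 start month. An onset without a year cannot qualify as a TEAE.

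These figures rest on the open-label reading of the first study dose, Period 2 start at Day 360, and uniform first-dose dates and event times. They are shares of partial dates, whose number is unknown and probably small. The rules should be corrected because complications are few and are analysed by period, arm and onset time; the documents do not show that any result will change materially.

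**What to change.** 1. **Period 2 anchor.** For randomised subjects, use it if the known date parts do not exclude onset on or after the Period 2 start, and neither the resolution date nor the date the site became aware is before that start. Then impute the later of the Period 2 start and the earliest date compatible with the recorded year and month. Otherwise apply the Period 1 anchor in the same way. Taking the later date matters: an onset recorded in May 2021 must stay in May 2021 and not move back to a Period 2 start in March 2020.
2. **Missing day.** Replace the second condition with a plain else.
3. **No onset date.** Count the AE as treatment-emergent in the period in which the site became aware of it, unless it resolved before treatment start. Protocol 12.2.4.1 already collects the awareness date.
4. **Complications.** State whether the date rules apply to the SAP 9.1 endpoint, given its sentence on missing data.

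The cost is a few lines of SAP text and minor programming, settled before unmasking. The downside should be stated: before the resolution-date and awareness-date limits, about 4% of day-missing and 51% of month-missing true Period 1 events would move into Period 2. These are open-label IKERVIS events, and under 3:2 allocation about 98/245 = 40% of them would be counted against Vehicle. Report a sensitivity count without the events placed in Period 2 by imputation.

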5.3. Multi-Center Studies

This study will be conducted in about 36 sites located in European and non-European countries. Sites will not be pooled for any inferential analysis.

5.4. Multiple Comparisons / Multiplicity

The objective of this study is to better understanding of long-term efficacy for exploratory purpose. No multiple comparison will be planned.

5.5. Interim Analysis

There is one interim analysis planned for this study. The purpose of the interim analysis is to present appropriate summary of data collected for the period 1. Interim analysis will be conducted once all subjects will have completed their Month 12 Visit or withdrawal visit.

Data cut criteria for this interim analysis is shown in Table 3.

Table 3 Data Cut Plan for Interim Analysis

Analysis Data	Data Example	Data Cut Criteria
Visit Data	IOP, TBUT, DEQS, etc. that are collected on visit date	Data collected at Month 12 or earlier will be included.
Non-visit Data	AE, medication, procedures, CSI, etc.	Incidents that happened up to the day of the first dose in Period 2 study drug will be included in the analysis.

Since the first 12 months of the study will be open-label study, no adjustment of alpha level and no Data Monitoring Committee will be needed for this study.

6. ANALYSIS POPULATION

Analysis populations defined for each analysis period are as follows.

For Period 1:

- The FAS (Full Analysis Set) Period 1 population consists of all enrolled subjects who received at least one dose of the study medication and had at least one post-baseline sign or symptom assessment of the study eye during Period 1. This will be the population used for efficacy analyses of Period 1.
- The **PPS** (**Per-Protocol Set**) **Period 1** will be a subset of FAS, restricted to the subjects who fulfill the protocol in the terms of the eligibility, interventions, and outcome assessment. It will be the analysis population for some sensitivity analyses.
- The **Safety Population Period 1** consists of all subjects enrolled in Period 1 who received at least one dose of the study medication and for whom any follow-up information is available. It will be the analysis population for safety analyses to be performed with subjects as treated.
- The **Sjögren Patients Population** consists of subjects who were known to have diagnostic status of the Sjögren disease based on the medical history obtained at baseline.
- The **Subjects Markedly Improved during Period 1** are defined as FAS subjects who achieve CFS score improvement from baseline of 2 grades or more (unless if the subject had a CFS score of 5 at baseline, the improvement in CFS has to be 3 grades or more) at anytime during Period 1.

For Period 2 and Entire Study:

- The FAS Period 2 (or FAS Entire Study) population consists of all randomized subjects who received at least one dose of the double-masked study medication and had at least one post-Month 12 sign or symptom assessment of the study eye during Period 2. This will be the population used for efficacy analyses.
- The **PPS Period 2 (or PPS Entire Study)** will be a subset of FAS Period 2, restricted to the subjects who fulfill the protocol in the terms of the eligibility, interventions, and outcome assessment. It will be the analysis population for some sensitivity analyses.
- The Safety Population Period 2 (or Safety Population Entire Study) consists of all subjects randomized in Period 2 who received at least one dose of the double-masked study medication and for whom any follow-up information is available in Period 2. It will be the analysis population for safety analyses to be performed with subjects as treated.
- The Sjögren Patients Population (Period 2 or Entire Study) consists of subjects who were known to have diagnostic status of the Sjögren disease based on the medical history obtained at baseline and satisfies FAS Period 2 or Safety Population Period2 criteria depending on analysis.

